Multicenter observational program VAP-PRO-C6

Protocol N° IC4-05682-066-RUS

NCT04757766

Effectiveness and tolerability of venoactive drugs in combination therapy and their effect on the overall treatment outcomes in patients with chronic venous diseases of CEAP classes C6 in real clinical practice.

23\12\2020

Multicenter Observational Program

VAP-PRO-C6

Protocol № IC4-05682-066-RUS

Effectiveness and tolerability of venoactive drugs in combination therapy and their effect on the overall treatment outcomes in patients with chronic venous diseases of CEAP classes C6 in real clinical practice

Rationale

Currently, about 40 million people in Russia, mostly of working-age population, suffer from various forms of chronic venous diseases (CVDs) [1].

Progressive trophic disorders of soft tissues in decompensated forms of CVD contribute to the development of long-term non-healing venous ulcers (VUs) and are the most common cause of this complication [2, 3].

The challenges in the treatment of patients with long-term non-healing VUs related to decompensated forms of chronic venous insufficiency (CVI) represent one of the urgent and socially significant problems in modern medicine.

The number of patients with VUs is growing steadily each year by 0.20 - 0.35% [4].

A high prevalence of trophic ulcers of venous etiology and their tendency to recur substantiate the need for using optimal combination of the most effective modern methods of treatment.

The local wound care and the use of compression therapy constitute the basis of standard treatment of VUs [5]. According to published data, the rate of ulcer healing with this standard treatment varies widely and ranges from 45% [6] to 83% [7] after 24 weeks of treatment. However, the medical costs associated with the long-term treatment of such chronic wounds are substantial [5,8]. These problems in the treatment of VUs have generated interest in the use of pharmacotherapy to accelerate their healing.

To date, there is no consensus on this topic, and a comprehensive staged approach is underused in the treatment of patients with VUs in routine clinical practice. All of this became a rationale to carry out the present study.

References

2. Savelyev V.S. Phlebology Moscow: 2001 [in Russ.]

2. Description of changes in the quality of life (QoL) measured by the CIVIQ-14 (3):

Variables:

- Global Index Score (GIS) of CIVIQ-14.

3. Description of the adherence to systemic pharmacotherapy as a part of the combination therapy in patients with VUs and CVD of CEAP class C6:

Variables:

- % of patients who continue to use the prescribed VAD at V1, V3 (interim), and V4 visits (if applicable)

^{*} Reference venous ulcer is a primary active venous ulcer, selected by investigator for the follow-up and reporting in the Case Report Form (CRF) in case several ulcers are present in the patient.

The reference VU should meet the following criteria:

- area is no less than 5 cm² but no more than 30 cm²
- phase 2 or 3 of the wound healing process;
- location on the medial aspect of lower third of leg.

- 1) Rutherford RB, Padberg FT Jr, Comerota AJ, Kistner RL, Meissner MH, Moneta GL; American Venous Forum's Ad Hoc Committee on Venous Outcomes Assessment: Venous severity scoring: An adjunct to venous outcome assessment. *J Vasc Surg* 2000;31:1307-1312.
- 4) https://ilyukhin.info/articles/lesionmeter - izmerenie_ploshhadi_jazv. Last accessed: July 7, 2020.

Methods

Each treating physician includes at least 5 patients in the program that meet the inclusion criteria. The inclusion period lasts for 6 months. The treatment will be consistent with routine clinical practice, local label for the medical use of drugs and the specific clinical situation. The following objective methods will be used to assess the changes in the skin condition:

- measurement of the area of reference ulcer (using LesionMeter[†]) before and after the treatment;
- changes in *status localis*.

Duplex ultrasound study (DUS):

- The presence and location of venous reflux and/or occlusion.

Important: Measurement data are recorded for the limb where the reference ulcer is located.

Please note, that DUS will be performed only at the inclusion visit to objectively confirm diagnosis of CVD. Once the diagnosis confirmed, further examination with DUS is not required without specific indications for reevaluation.

Patient management

The study does not implicate any intervention to routine management of patients with chronic venous disease (CVD). In particular, in this study the parameters that are usually evaluated during the examination of patients with classes C6 CVD (CEAP) will be recorded. Special attention will be paid to evaluating changes of the area of referent VU using objective methods (measuring ulcer area using LesionMeter, time to ulcer healing).

Treatment

The observational nature of the program implies that all examinations, procedures and changes in the treatment of patients, including changes in the dosing regimen, should be carried out only on the basis of judgment of the treating physician and in full compliance with the guidelines on the treatment of patients with CVD, local labels for medical use of drugs, and in the settings of daily routine practice.

[†] LesionMeter is a generally available tool for measuring the venous ulcer area.

Therapy is conducted in full accordance with existing guidelines. The patient's participation in the program, as well as his/her refusal to continue such participation, should not affect the current treatment, the availability of diagnostic procedures or the volume and quality of other necessary medical care.

The names and doses of drugs used for the CVD treatment, as well as changes in their doses will be recorded in the Case Report Form.

Inclusion criteria:

- CVD documented by venous DUS
- Age over 18 years
- Written informed consent is provided
- No treatment with venoactive drugs within 4 weeks prior to inclusion in the study
- Presence of a primary /active venous ulcer (class C6/ CEAP) that meets criteria for the referent ulcer
- No surgical intervention or procedure (including sclerotherapy) for CVD is planned

Non-inclusion criteria:

- Obliterating atherosclerosis
- Lymphatic edema of the lower extremities
- Angiodysplasia, neoplasia
- Peripheral artery disease (ankle-brachial index 0,8-1,3)
- Infectious process in the previous 6 weeks
- The presence of one or more comorbidities in the patient that can affect the results:
 - ✓ Connective tissue diseases (including rheumatoid arthritis, arthritis)
 - ✓ Chronic heart failure 3-4 function class (NYHA)
 - ✓ Chronic kidney disease
 - ✓ Diabetes mellitus experience of at least 10 years and more or Diabetes mellitus experience less than 10 years, but decompensated. Diabetic foot.
 - ✓ Skin diseases of non-venous origin
 - ✓ Intermittent claudication (peripheral artery disease)
 - ✓ Diseases of bones or joints of the lower limbs, that can affect the course of the ulcer according to the researcher
 - ✓ Malignant neoplasm
- Treatment with drugs that can cause edema of the lower extremities (calcium channel blockers, hormonal agents, NSAIDs, etc.)
- History of deep vein thrombosis (within 1 year prior to inclusion)
- History of superficial venous thrombophlebitis (within 3 months prior to inclusion)
- The patient underwent surgery for CVD in the previous 3 months
- Patient cannot walk (regardless of the cause)
- Poor predicted adherence to treatment
- Participation in an intervention study in the previous 3 months
- For women: pregnancy or breastfeeding, or willing to become pregnant within at least 2 months after the end of the study
- The necessity, according to the doctor-investigator, of treatment with any diosmin-containing drug outside of its approved indications (off-label) or in the presence of contraindications stated in the instruction for medical use of this drug relevant in the Russian Federation at the time of the study, within the scope of this protocol
- Use of a topical agent that is contraindicated in case of compromised skin integrity

Exclusion criteria:

- Withdrawal of the informed consent
- Pregnancy or willingness to become pregnant within at least 2 months after the end of the study
- Indications for surgery (including sclerotherapy)
- Serious violation or non adherence to the prescribed therapy/ regimen
- Use of prohibited drugs that can cause edema of lower extremities (calcium channel blockers, hormonal agents, NSAIDs, etc.)

Treatment effectiveness criteria

1. Venous Clinical Severity Score (VCSS)
2. Clinical class of CVD by CEAP classification (2020)
3. Changes in the parameters of skin condition:
 - area of the reference venous ulcer (measured by LesionMeter)
 - changes in *status localis*
 - changes in symptoms (pain) as assessed by visual analogue scale (VAS).
4. The quality of life (QoL) questionnaire CIVIQ-14 (**Appendix 2**).

Data collection during the study

At scheduled visits participating physicians will be assessing and collecting parameters of interest which they should input in eCRF.

At the inclusion visit (V0) following data will be collected: a signed consent form, demographic characteristics (age, sex, body weight, BMI and height), eligibility of a patient to the inclusion/ non inclusion criteria, history and risk factors of CVD, history and current status of taking drugs and non drug treatments for CVD; all parameters of VCCS including characteristics of symptoms for CVD such as pain, hyperaemia, characteristics of the ulcer(s) etc., characteristics of the reference ulcer; results of evaluation of the stage of the disease (CEAP classification); results of DUS characterizing venous reflux and its location, presence or absence of venous occlusion and its location; skin condition/ pain severity will be patient-reported evaluation with VAS, results of a self-assessed quality of life status performed by completing CIVIQ 14 questionnaire; assigned treatment for CVD including data on administered topicals, systematic pharmacotherapy, compression therapy.

At visits 1; 2; 3 (V1; V2;V3) following data will be collected: eligibility of a patient to exclusion criteria; characteristics of the ulcer(s) etc., characteristics of the reference ulcer; skin condition/ pain severity will be patient-reported evaluation with VAS; any changes in the administered treatment for CVD including usage of topicals, usage of systematic pharmacotherapy, usage of compression therapy; information regarding any adverse event/ adverse drug reaction or special situations (see chapter Safety Considerations).

At visit 4 (V4) following data will be collected: eligibility of a patient to exclusion criteria; all parameters of VCCS including characteristics of symptoms for CVD such as pain, hyperaemia, characteristics of the ulcer (s) etc., characteristics of the reference ulcer; results of evaluation of the stage of the disease (CEAP classification); skin condition/ pain severity will be patient-reported evaluation with VAS; results of a self-assessed quality of life status performed by

completing CIVIQ 14 questionnaire; any changes in the administered treatment for CVD including usage of topicals, usage of systematic pharmacotherapy, usage of compression therapy; information regarding any adverse event/ adverse drug reactions or special situations (see chapter Safety Considerations).

SCHEDULE OF THE STUDY

Actions	V0 visit (inclusion)	V1 visit (1 month after V0 visit)	V2 visit (3 months after V0 visit)**	V3 visit (interim), if applicable*	V4 visit (6 months after V0 visit)
Informed consent	+				
Inclusion/ Non inclusion criteria	+				
Exclusion criteria		+	+	+	+
Reporting of AEs		+	+	+	+
Completion of the CRF	+	+	+	+	+
VCSS	+				+
CEAP clinical class	+				+
Skin changes (by VAS)	+	+	+	+	+
Status localis	+	+	+	+	+
DUS (presence of reflux)	+				
QoL assessment (CIVIQ-14)	+				+
Data on the treatment and its change	+	+	+	+	+
Venoactive drug	+	+	+	+	+
Compression hosiery	+	+	+	+	+
Topical treatment	+	+	+	+	+

* The visit takes place if the venous ulcer is healed between V2 and V4 visits

**The visit can be replaced by telephone interview which remains at discretion of the doctor-investigator

Safety considerations.

1. Definitions

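### The adherence variable's only reading between month 1 and month 6 comes from V3, a visit held only for patients who heal between V2 and V4, while the month-3 reading at V2 goes unused

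*Combined protocol and SAP*

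**What the plan says.** Under Secondary goals, item 3, the adherence variable is the percentage "of patients who continue to use the prescribed VAD at V1, V3 (interim), and V4 visits (if applicable". V2 is not in the list, and no denominator is given.

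The Schedule of the study table sets the visits as follows:

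- "V1 visit (1 month after V0 visit" and "V4 visit (6 months after V0 visit": fixed times, with no condition on healing.
- "V2 visit (3 months after V0 visit": a fixed time, with no condition on healing. A footnote adds: "The visit can be replaced by telephone interview which remains at discretion of the doctor-investigator".
- "V3 visit (interim), if applicable": no fixed time. Its footnote reads: "The visit takes place if the venous ulcer is healed between V2 and V4 visits".

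The same table marks the rows for venoactive drug and for treatment data at every visit, V2 included. The section Data collection during the study agrees. For V1, V2 and V3 alike it lists "any changes in the administered treatment for CVD including usage of topicals, usage of systematic pharmacotherapy" among the items recorded.

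Two further passages bear on the point. The Exclusion criteria include serious non-adherence to the prescribed therapy, and the schedule checks these criteria from V1 to V4. Statistical parameters plans comparisons between groups that differ in adherence, but does not say which visit, or which rule, defines those groups.

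**The concern.** A percentage describes the patients in its denominator. At V1 and V4 these are the patients in follow-up, whatever the state of their ulcer. At V3 they are only those whose ulcer healed in one three-month window. Healing of the reference ulcer is itself the first primary variable, so V3 selects patients on the outcome of the study.

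Two groups have no V3: patients who have not healed by V4, and patients who had already healed by V2. The variable gives neither group a reading in the five months between V1 and V4. V3 also has no set date, so its percentage pools readings taken at any time from month 3 to month 6.

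If the three percentages are printed in a row, a reader will take them as a sequence over time. The middle figure would describe different patients from the figures on either side, and a rise or fall at V3 could reflect who was there and not a change in drug use. A reading without this defect exists at V2, and the variable does not use it.

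**Working it through.** The documents give no adherence rate and no precision target, so there is no figure to reproduce. The check is first structural, then a sizing of the V3 subset.

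**Step 1: visits side by side**

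| Visit | Time | Condition on healing | VAD use recorded | In the adherence variable |
|---|---|---|---|---|
| V1 | month 1 | none | yes | yes |
| V2 | month 3 | none | yes | no |
| V3 | not fixed, months 3 to 6 | healed between V2 and V4 | yes | yes |
| V4 | month 6 | none | yes | yes |

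V2 is the only visit free of a healing condition that the variable omits. No other section adds it or explains the omission.

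**Step 2: how many patients V3 could hold**

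Inputs:

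- N = 450 planned patients (Design).
- h = proportion healed at 24 weeks, 0.45 to 0.83 (Rationale, cited for standard local care and compression).
- f = share of those healers already healed by V2. The documents do not give it; assumed range 0 to 0.75.
- Dropout is ignored.

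Formulas: V3 count n = N × h × (1 − f). V3 share s = n / N. Unhealed at 6 months = N × (1 − h). Healed by V2 = N × h × f.

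- h = 0.45, f = 0: 450 × 0.45 × 1 = 202.5 (45%).
- h = 0.45, f = 0.75: 450 × 0.45 × 0.25 = 50.6 (11.25%).
- h = 0.83, f = 0: 450 × 0.83 × 1 = 373.5 (83%).
- h = 0.83, f = 0.75: 450 × 0.83 × 0.25 = 93.4 (20.75%).

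Unhealed at 6 months, and so without a V3: 450 × 0.55 = 247.5 at the lower healing rate and 450 × 0.17 = 76.5 at the higher. Healed by V2 at f = 0.75, and also without a V3: 151.9 and 280.1.

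**Step 3: precision**

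At an assumed 80% adherence, the 95% half-width is 1.96 × √(0.8 × 0.2 / n). With n = 450 at V2 it is 3.7 percentage points. At V3 it is 5.5 (n = 202.5), 11.0 (n = 50.6), 4.1 (n = 373.5) and 8.1 (n = 93.4).

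**Step 4: how far the V3 figure could stand from the whole cohort**

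If V3 patients and all others differ by d points in adherence, the V3 figure minus the all-patient figure is d × (1 − s). With an assumed d = 20 (90% against 70%):

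- h = 0.45: 20 × 0.55 = 11.0 at f = 0, and 20 × 0.8875 = 17.75 at f = 0.75.
- h = 0.83: 20 × 0.17 = 3.4 at f = 0, and 20 × 0.7925 = 15.85 at f = 0.75.

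If the rates are reversed (70% against 90%), the gaps keep their size and change sign. Nothing in the documents fixes d or its sign. Adherent patients may heal more often, or patients may stop the drug once healed. Step 4 is an illustration and not an estimate of bias.

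**The case against.** The best defence is that the variable is descriptive. No section plans a trend across V1, V3 and V4, a test between visits, or a comparison of V3 with either neighbour. The words in brackets at the end of the variable match the label of V3 in the schedule and signal that not every patient contributes. Drug use at the healing visit is a legitimate thing to describe if it is labelled as such. This stands in part. The wording concedes that V3 is conditional, but it gives no denominator and no label, and it does not bring V2 back.

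Three stronger readings are tempting, and the documents support none of them.

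- A reader might infer that adherence in unhealed patients goes unobserved between month 1 and month 6. It does not: the schedule and the data-collection text both record drug use at V2, and a telephone contact does not prevent the question. Only the defined variable has the gap.
- A reader might infer that the V3 figure will overstate adherence, or that the documents show a bias of known size. They give neither direction nor size.
- A reader might infer that the planned comparisons between adherence groups are conditioned on healing. That would follow only if V3 defined the groups, and Statistical parameters does not say so.

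It is also fair to say that adding V2 does not by itself give a clean course over time. Patients with serious non-adherence can be excluded at any visit from V1, and would then drop out of later readings unless the denominator keeps them.

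**Conclusion.** The point holds as a defect in the definition of one secondary variable. Read as written, its only figure between month 1 and month 6 comes from patients who healed between V2 and V4, at no fixed time. It omits both those unhealed at V4 and those healed by V2. The readings at V1 and V4 are not affected.

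The V3 subset would be about 51 to 374 of 450 patients. This rests on the protocol's cited healing range, an assumed 0 to 75% of healers healed by V2, and no dropout. The range shows how selective the visit could be; it does not measure distortion.

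The change should be made, because it alters a reported secondary result and uses data already planned. It does not touch the primary goal.

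**What to change.** - Define the variable as the percentage of patients continuing the prescribed VAD at V1, V2 and V4, using the drug-use data already recorded at V2, in person or by telephone.
- Take all patients prescribed a VAD at V0 as the denominator at each visit. Count patients excluded for non-adherence as not continuing. Show other withdrawals and missing readings in separate rows.
- Report drug use at V3 in its own line, labelled as the subset healed between V2 and V4, with its count.
- Tabulate stopping before and after healing only as far as the visit-level data allow. The documents mention drugs, doses and changes but do not clearly provide for a stop date, so the order of stopping and healing may not be known for every patient.

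The cost is a reworded variable, a short rule for the denominator and one extra table line. The V1, V2 and V4 percentages need no new visit, procedure or data item, and patient management does not change.

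### The peripheral artery disease non-inclusion line gives an ankle-brachial index range without saying whether that range bars or admits a patient

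*Combined protocol and SAP*

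**What the plan says.** The Non-inclusion criteria section contains the line "Peripheral artery disease (ankle-brachial index 0,8-1,3". The bracket holds a two-sided range and nothing else: no comparison sign, and no word marking the range as excluded, required or allowed.

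Three other lines in that section bear on the same patients, none with an index value: "Obliterating atherosclerosis", "Intermittent claudication (peripheral artery disease" and "Skin diseases of non-venous origin". The Inclusion criteria section also requires a venous ulcer: "Presence of a primary /active venous ulcer (class C6/ CEAP) that meets criteria for the referent ulcer".

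The ankle-brachial index is not mentioned again. It is absent from the inclusion criteria, from the V0 items under Data collection during the study, and from the visit schedule, whose only vascular test is duplex ultrasound for venous reflux. Eligibility as such is a listed V0 item.

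**The concern.** An eligibility line should give the same answer whoever applies it. This one is to be applied by about 90 phlebologists in 60 cities (Design section), and it supports opposite decisions on the same patient.

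Three things could follow: patients the sponsor wanted are turned away; patients with arterial disease that is neither diagnosed nor symptomatic are let in; or sites screen differently. The first primary variable is the percentage of patients whose reference ulcer has healed completely at 6 months. A descriptive percentage is only as clear as the population it describes, and this line leaves part of that population undefined. The index value is not a listed V0 item, so on the listed data nobody could later tell which reading a site had used.

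**Working it through.** The plan has no figure to reproduce here, and the check is logical. The inputs are the line itself, the rest of the Non-inclusion criteria list, and the reference-ulcer definition that follows the Secondary goals.

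**Step 1. Possible readings.**
- A: an index inside 0.8–1.3 bars the patient.
- B: 0.8–1.3 is the admissible range and a word is missing, so an index outside it bars.
- C: the diagnosis bars on its own and the range is only a note.
- D: the diagnosis and an index inside the range must both be present to bar.

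**Step 2. Is the patient barred by this line alone?** The three zones cover every index value.

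| Arterial diagnosis | Reading | Below 0.8 | 0.8–1.3 | Above 1.3 |
|---|---|---|---|---|
| Absent | A | no | yes | no |
| Absent | B | yes | no | yes |
| Absent | C | no | no | no |
| Absent | D | no | no | no |
| Present | A | no | yes | no |
| Present | B | yes | no | yes |
| Present | C | yes | yes | yes |
| Present | D | no | yes | no |

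There are 2 × 3 = 6 combinations of diagnosis and zone. A and B give opposite answers in all 6, so the four readings never all agree. For a patient without a diagnosis they reduce to three different rules, because C and D both bar nobody.

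**Step 3. Each reading against the label.** An index of 1.0 means equal ankle and arm pressures. Under A that patient is barred, while an index below 0.8 or above 1.3 passes, under a line headed peripheral artery disease. Under D, diagnosed patients outside the range pass this line, although "Obliterating atherosclerosis" and "Intermittent claudication (peripheral artery disease" bar with no index condition. Under C the figures do nothing. Under B the decisive word is absent.

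**Step 4. Does the rest of the list settle it?** Eight other non-inclusion lines carry a number:

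1. infectious process, 6 weeks
2. "Chronic heart failure 3-4 function class (NYHA"
3. diabetes, 10 years
4. "History of deep vein thrombosis (within 1 year prior to inclusion"
5. "History of superficial venous thrombophlebitis (within 3 months prior to inclusion"
6. surgery for chronic venous disease, 3 months
7. participation in an intervention study, 3 months
8. intention to become pregnant, 2 months

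In 8 of 8 the number describes patients to be barred. That convention points to A or D, the readings under which an index below 0.8 is not caught. Where the protocol does mean an admissible range, as for the reference-ulcer area (5 to 30 cm²), it states the direction of both limits. The pattern is suggestive and does not prove what was meant.

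**Step 5. Who is exposed.** The lines on atherosclerosis, claudication and non-venous skin disease would catch many arterial patients under any reading, and a venous ulcer is required. What remains is mainly patients with no arterial diagnosis and no arterial symptoms.

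**Step 6. Can it be counted?** No. The documents give neither the number screened nor a distribution of the index, and the planned 450 counts included patients only.

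**The case against.** The strongest reply is that the line names a diagnosis and adds the index only in brackets, so a patient without peripheral artery disease and with an index of 1.0 is barred under reading A alone. That is correct, and the 1.0 example should be read as belonging to A. It does not rescue the line, since A is one of the open readings and each of the others has its own fault (step 3).

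It can also be said that the section heading gives a direction, so the text is not wholly silent. But that direction leads to A or D, and both let patients outside the range pass a line meant to bar arterial disease.

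The 8-of-8 pattern is weak evidence. Seven of the eight numbers are time periods and one is an ordinal class; none is a two-sided range of a measured ratio. The diabetes line is not a clean limit either, because shorter disease also bars if decompensated. The contrast with the ulcer-area criterion is a single example from another list. All of this stands. The pattern shows only that the list does not resolve the question in favour of the admissible-range reading.

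Finally, the consequences are possible rather than shown. The readers are specialists, the eCRF is not among the documents and may settle the matter, the index enters no analysis, and the planned 450 is not shown to depend on it. This too stands, and it limits how serious the point can be. It does not remove the need to correct the line.

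**Conclusion.** The concern holds: the line is wrong as written. Confidence is high that its meaning is not fixed by the documents. The two main readings, A and B, give opposite decisions at every index value, and no other text chooses between them.

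The size of the effect is unknown. No patient count, and no direction or amount of change in the 6-month healing percentage, can be derived. Exposure is limited by the other arterial lines and the venous-ulcer requirement. The point should be fixed, but it does not undermine the program. The conclusion rests on the protocol's wording alone; it assumes no outside reference value for the index and takes no position on which limits are clinically right.

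**What to change.** The sponsor should reconcile the label, the range and the list in which the line stands:

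- State whether 0.8–1.3 is the barred or the admissible range, giving the direction in words as the ulcer-area criterion does.
- State whether the index alone decides or only together with a diagnosis.
- Have the sponsor's clinicians confirm the limits.
- Align the atherosclerosis and claudication lines, and any eCRF eligibility check, with the corrected text.

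Optionally, where the index is already measured in routine practice, record its value at V0 so that eligibility can be verified afterwards. Limiting this to existing measurements keeps the program observational.

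The core change costs one line of protocol text and matching wording in any eCRF check. The planned number of patients and the analyses are unaffected.
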